2.0 Study Summary

2.1 Study Title: Hydroxychloroquine vs. Azithromycin for Hospitalized Patients with Suspected or Confirmed COVID-19 (HAHPS).

2.2 Study Objective: Assess the efficacy and safety of hydroxychloroquine (HCQ) as opposed to azithromycin for suspected or confirmed COVID-19.

2.3 Study Hypothesis: Hydroxychloroquine is superior to azithromycin in improving outcomes among patients with suspected or confirmed COVID-19.

2.4 Study design: Phase 2 prospective, randomized, open-label active comparator trial.

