5.0 Study Procedures

Note that given the high contagiousness of SARS-CoV-2, the limited supply of personal protective equipment, and risk to coordinators' health, study visits, procedures, and monitoring will be performed in a no-touch mode. This also applies to the consenting process, which will be performed via a consenting mechanism that confirms the identity of the patient, provides access to the consent form, and obtains a signature to complete documentation, without requiring physical proximity of research staff and the study subject.

5.1 Study commencement. After informed consent and enrollment, coordinators will complete the baseline CRF, and initiate study procedures, including randomization (variable permuted block randomization by hospital).

5.2 Study drug. This is an open label, randomized, active comparator trial. Patients who are discharged home will not continue treatment after hospital discharge. If the patient has already received azithromycin or hydroxychloroquine prior to randomization (no more than 2 days), the prior doses will count toward the 5-day total dose. For enrolled patients whose laboratory testing returns negative for SARS-CoV-2, if the clinical team believes that another cause of the patient's presentation is more likely than COVID-19 in light of the negative laboratory testing, the clinical team may stop study drug. Such discontinuation will be recorded. Since the fundamental clinical question is whether to start treatment in patients with suspected or confirmed COVID-19, these patients will remain in the primary analytic cohort.

The trial will be temporarily suspended for enrollment at a given site in the event that no study drug is available at that site.

5.2.1. Hydroxychloroquine. Patients in the hydroxychloroquine arm will receive hydroxychloroquine 400mg po BID x 1 day, then 200mg po BID x 4 days³ (dose reductions for weight < 45kg or GFR<50ml/min). For patients < 45kg, doses will be halved. For patients with GFR<50ml/min, the final dose of hydroxychloroquine will not be administered. The drug dose chosen falls at the lower end of doses proposed in various international trials, but it has proven in vitro efficacy, with a ratio of lung tissue trough concentrations to the EC50 (effective concentration to suppress 50% of viral activity) of >20.³ Given in vitro confirmation of the adequacy of the dose and likely superior safety profile at the lower dose, we chose the total dose of 2.4gm over 5 days.

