discharge. This approach will be used because persisting limitations are unlikely to have resolved and then recurred by 14 days. Similar single imputation rules will be devised for sensitivity analyses of secondary efficacy endpoints consistent with prior practice in the field and will be determined before the given analysis is performed to avoid bias from knowledge of outcomes.

Safety reporting

The HAHPs trial uses the adverse event reporting developed for the PROWESS-SHOCK trial.^{7,8} This approach is based on the high incidence of conditions resulting from the underlying disease that would be classified as adverse events if they occurred in healthy outpatients but are unlikely to be related to the study drug. Instead of being classified as adverse events, such events are monitored as study clinical or safety outcomes (Table 2). The exception to this rule are events which are either serious and study-related or which lead to permanent discontinuation of study drug. Those latter are reported as adverse events and are classified within the MedDRA taxonomy.

For reporting purposes, for each safety outcome or adverse event each patient will be classified as having experienced the outcome at least once (vs. never having experienced the outcome). We will separately provide counts (proportions) of safety outcomes and individual adverse events. In early interim analyses, comparisons of safety outcomes between treatment groups will be viewed as primarily descriptive. However, we will provide nominal p-values to compare adverse events and safety outcomes between groups without multiple comparison adjustment using the Chi square or Fisher exact test as appropriate to provide a crude assessment of the compatibility of observed differences between treatment groups with chance. Isolated p-values which are < 0.05 will be interpreted recognizing that 5% of such p-values will reach this threshold by chance in the absence of an actual effect of the treatment.

QTc was monitored at 24–48h after randomization as a study procedure. QTc monitoring at baseline was not mandatory but was described where it was available. We also described the change between baseline and 24–48h after randomization in QTc. These results will be summarized HAHPs SAP

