Under the Bayesian design, the posterior distribution describing the accumulating evidence provided by the data for treatment benefit or harm was updated at successive interim analyses during the trial.⁹ After consultation with the DSMB and consistent with the DSMB charter written before the first interim analysis, we performed interim analyses after enrollment of every 60 patients. This cadence for interim analyses was confirmed through simulation to yield performance characteristics consistent with a trial-wise alpha of approximately 0.05 if a frequentist approach had been taken.¹⁰ We adopted a Bayesian approach to allow the DSMB to recommend continuation or closure of the trial based on the totality of evidence, including data from the present trial and from other relevant experiments or trials. While the trial is not designed to be stopped for futility based on the trial data alone, the DSMB is authorized to incorporate the totality of evidence in making decisions about recommending closure of the trial to further enrollment.

Sample size and power. We generated an approximate sample size and power calculation by providing the odds ratios closest to 1 (corresponding to the minimum detectable treatment effects, which are indicated by odds ratios less than 1, reflecting treatment benefit for hydroxychloroquine over azithromycin) which can be detected in a frequentist analysis of the primary outcome under a proportional model without covariate adjustment. The target sample size of this trial is 300 randomized subjects; Table 4 also considers smaller sample sizes to indicate the power the trial will reach under various scenarios for enrollment depending on state-wide disease dynamics. The power calculations were performed using statistical simulation (N=10,000 simulations per combination of parameters), and provide results very close to those provided by an approximation provided by Whitehead.¹¹ For the sample size calculation, we considered three scenarios for the distribution in the azithromycin group for the 8 categories of the COVID Ordinal Outcomes Scale: Scenario 1: Uniform distribution with probabilities of 0.125 for each score level, Scenario 2: Overall probabilities at 14 days HAHPS SAP

averaging across both groups of the recent COVID-19 trial by Cao et al.¹² (1= 0, 2= 0.36, 3=0.16, 4=0.23, 5=0.05, 6=0.02, 7=0.02, 8=0.16), and Scenario 3, with probabilities averaged between Scenarios 1 and 2.

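### For the Table 2 safety outcomes and adverse events, the SAP plans a p-value but no effect estimate or interval; risk differences with 95% intervals would be a cheap improvement

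*SAP*

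**What the plan says.** Protocol section 2.2 makes safety part of the objective: "Assess the efficacy and safety of hydroxychloroquine (HCQ) as opposed to azithromycin". (Section 3.3 restates the objective with efficacy only.)

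The SAP's Safety reporting section classifies each patient as ever or never having had each outcome. It then plans two things:

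- Description: "We will separately provide counts (proportions) of safety outcomes and individual adverse events".
- Comparison: "we will provide nominal p-values to compare adverse events and safety outcomes between groups without multiple comparison adjustment". Each p-value comes from a chi-square or Fisher test, whichever suits, and the SAP itself regards the result as only a crude check against chance.

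Its one rule of interpretation is "Isolated p-values which are < 0.05 will be interpreted recognizing that 5% of such p-values will reach this threshold by chance". The Safety paragraph of protocol section 5.7 plans counts and proportions only.

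Neither document names a risk difference, risk ratio, odds ratio, interval or margin for these outcomes. By contrast, the SAP's Primary Analysis and Secondary Analyses sections attach 95% credible intervals to the efficacy odds ratios. Follow-up QTc is handled apart from Table 2, by analysis of covariance or a t-test.

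**The concern.** A p-value answers one question: whether a difference of the observed size would be surprising if the arms were alike. It does not say how large a harm the data leave open. For frequent outcomes in a large trial the two questions tend to get similar answers. For uncommon outcomes in a trial of at most 300 patients they do not, because the test is usually non-significant whether or not a harm exists.

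Several Table 2 outcomes with a plausible drug link (arrhythmia, cardiac arrest, seizure, symptomatic hypoglycemia, C. difficile infection) may be uncommon over the five days in which Table 2 is measured. Protocol sections 5.4 and 5.4.1 describe the drugs' side effects as rare. The SAP's one caution concerns false positives; nothing addresses false negatives. At stake is how far the trial's safety statement can be taken.

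**Working it through.** **Inputs.** From the documents: "The target sample size of this trial is 300 randomized subjects", which protocol section 2.7 treats as a maximum; a safety population limited to patients who received at least one dose; a threshold of 0.05; and chi-square or Fisher tests. My assumptions: two-sided tests; 1:1 allocation, since the protocol gives "variable permuted block randomization by hospital" but no ratio; hence 150 per arm as the best case; Fisher used when an expected cell is below 5 and uncorrected chi-square otherwise, as a reading of the SAP's loose choice rule; and control rates of 1% to 10%, since the documents give none.

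**1. The plan's own figure.** There is no power or precision figure for safety, so the check is on the efficacy table. With the Whitehead formula, V = N(1 − Σp̄³)/12, N = 300 × 0.95 = 285, and power = Φ(|log OR|·√V − 1.96).

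- Scenario 1 at OR 0.56: Σp̄³ = 0.017, V = 285 × 0.983/12 = 23.35, √V = 4.83, |log 0.56| = 0.580. Power = Φ(2.80 − 1.96) = 80%.
- Solving for 80% power gives 0.560, 0.546 and 0.557 for the three scenarios, against 0.56, 0.55 and 0.55 in SAP Table 4. The N = 300 row reproduces.

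**2. Chance of missing a doubling.** By the normal approximation at 5% vs 10%, p̄ = 0.075:

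- null standard error = √(2 × 0.075 × 0.925/150) = 0.0304
- alternative standard error = √((0.05 × 0.95 + 0.10 × 0.90)/150) = 0.0303
- power = Φ((0.05 − 1.96 × 0.0304)/0.0303) = 0.375

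Exact enumeration of the two binomials, with the test choice above, gives:

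| Control vs doubled rate | Power | Missed |
|---|---|---|
| 1% vs 2% | 2.3% | 98% |
| 2% vs 4% | 12.0% | 88% |
| 5% vs 10% | 37.0% | 63% |
| 10% vs 20% | 68.6% | 31% |

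By the approximation, power passes 50% at a control rate of about 6.9% and 80% at about 12.6%. For 80% power, 5% vs 10% needs 435 per arm and 2% vs 4% needs 1141.

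**3. What an interval adds.** Take 6/150 on hydroxychloroquine and 3/150 on azithromycin.

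- Fisher p = 0.50.
- Risk difference = 0.040 − 0.020 = +2.0 points.
- Wilson limits are 1.85% to 8.45% and 0.68% to 5.71%.
- Newcombe lower limit = 0.020 − √((0.0400 − 0.0185)² + (0.0571 − 0.0200)²) = −0.023.
- Newcombe upper limit = 0.020 + √((0.0845 − 0.0400)² + (0.0200 − 0.0068)²) = +0.066.
- Risk ratio 2.0, score interval about 0.56 to 7.2.

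The p-value reads as compatible with chance. The interval shows that an excess of 6 points, or a several-fold risk, has not been excluded.

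**4. The SAP's 5% statement.** Under no effect, with the same test choice, the chance of p < 0.05 is about 0.2% at a 1% event rate, 1.3% at 2%, 2.9% at 3% and 4.7% at 5%. The statement that "5% of such p-values will reach this threshold by chance" is clearly too high only at rates of about 3% or less.

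**The case against.** The strongest reply is that the low power comes from the sample size and the event rates, not from the choice of statistic. That is correct: the table in step 2 is the same with or without an interval, and only step 3 shows what the change buys. A reader might infer that the p-value causes harms to be missed, or that intervals would find them. Neither follows.

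Second, the SAP calls its p-values nominal and crude, and commits to counts by arm from which anyone can compute an interval. A reader might infer that the plan treats p > 0.05 as proof of safety. It never says so; the gap is that nothing warns against that reading. That readers can do the arithmetic themselves softens the point but does not remove it, because the plan already chooses a comparative statistic to print.

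Third, not all of Table 2 is rare. It includes elevated liver tests, cytopenias and nausea or vomiting, and the SAP justifies its approach by the high incidence of events due to the underlying illness. At control rates near 13% or above, a doubling is detected at least 80% of the time. The point is therefore confined to uncommon outcomes.

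Fourth, other harm analyses exist: the QTc comparison; the posterior probabilities of any and of moderate harm on the ordinal scale, which includes death and ventilation; exploratory displays by drug actually received; and investigation of SUSARs. These stand, but none puts an interval on arrhythmia, seizure, hypoglycemia or C. difficile infection.

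The SAP's description of safety comparisons as mainly descriptive is limited to early interim analyses, and the p-values follow directly after it.

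**Conclusion.** The concern holds as a cheap improvement in reporting. For Table 2 outcomes and adverse events, the plan's only between-arm statistic is a nominal p-value, while efficacy gets estimates with 95% credible intervals. At a best case of 150 per arm, a doubling is missed in most trials when the control rate is below about 7%, so a non-significant result there excludes little. The size rests on assumed event rates, 1:1 allocation and the assumed rule for choosing the test. Stopping before 300 patients would make it worse.

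It is not an error in a decision rule, endpoint or analysis set, and it does not undermine the efficacy analysis. A reader might also infer that the SAP's 5% remark is wrong throughout. It is close to right at event rates of 5% and above, so rewording it is optional.

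**What to change.** In the SAP's Safety reporting section:

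- For each Table 2 outcome and each adverse-event category, report the risk difference (hydroxychloroquine minus azithromycin) with a 95% Newcombe or score interval. Keep the p-value as secondary.
- State that a non-significant p-value will not be read as evidence of comparable safety.
- Optionally, change the false-positive remark to say at most about 5%, and less for outcomes with event rates of about 3% or below.

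The cost is some SAP wording and one more column in the safety tables, with no new data. Effect estimates with intervals would also serve the later meta-analyses that both documents anticipate. The downside is a safety statement that looks less reassuring.

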Meier curves. Patients who die prior to day 28 are assigned an artificial follow-up time of 28 days censored at that point. This will assign to these patients a worse outcome than any surviving patients, and avoid conflating prolonged hospitalization with death. Descriptively, these time-to-event endpoints will be displayed as median (IQR). If fewer than half of patients meet the event before censoring, we will choose an appropriate quantile (e.g., first quartile) for description and display the proportions with events during the respective weeks of follow-up. For the sake of consistency, we will use the same ordinal regression model with the same prior distribution for the odds ratio as was used for the primary analysis to generate median posterior odds ratios and credible intervals for these endpoints.

Sub-groups. On a purely exploratory level, we will summarize effect variation in sub-groups defined by (a) age \geq 65 years, (b) symptom duration \geq 10 days, (c) in ICU at enrollment, (d) presence of at least one comorbidity, (e) race/ethnicity, and (f) receipt of any clinical azithromycin before enrollment. At early interim analyses, the sample size will be too small to support meaningful statistical inference, and we will limit presentation of results in sub-groups to descriptive summaries using the summary measures described for each outcome above.

Missing Data. We expect fewer than 5% of subjects will have missing data on either the primary or key secondary outcomes listed above. Hence, our primary analyses will be restricted to non-missing observations, without imputation. For the primary outcome, a sensitivity analysis will be performed by applying single imputation. Where daily COVID Ordinal Outcomes Scale scores are missing after hospital discharge, we will use last carried forward with the following modifications—patients discharged to a facility other than home will be classified as “home with limitations” (score 2), and patients found subsequently to be home with limitations will be rated as “home with limitations” from hospital discharge through that follow-up point. Patients who are discharged to home and found to have no limitations at day 14 will be rated as “home without” limitations starting at the time of hospital HAHPS SAP

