descriptively by treatment group. If the baseline QTc is available in at least 80% of participants, an analysis of covariance will be performed to compare follow-up QTc between treatment groups with adjustment for baseline QTc. Otherwise, a 2-sample t-test will be used to compare the follow-up QTc levels.

Table 2 Safety outcomes (measured daily for first five days)
Death unrelated to study drug or procedures
Seizure
Receipt of vasopressors
Atrial or ventricular arrhythmia
Cardiomyopathy
cardiac arrest
Hypoxemia requiring supplemental oxygen
ARDS
Mechanical ventilation
ECMO
Elevated LFTs
Pancreatitis
Acute kidney injury
Renal replacement therapy
Symptomatic hypoglycemia
Hematologic or coagulation events
Cytopenias
Severe dermatologic reaction

Nausea/vomiting
Visual changes
C. diff infection

Concomitant medications

The classes of concomitant medications listed in Table 3 were measured at baseline (before randomization) and through day 5 after randomization. Concomitant medications will be descriptively summarized overall and by treatment group. In addition, some patients in the hydroxychloroquine arm received azithromycin either before or in some cases after randomization. The proportion receiving azithromycin was recorded, and in exploratory summaries, safety outcomes will be displayed in that group as well as in the groups who received only azithromycin or only hydroxychloroquine.

Table 3. Concomitant medications
ACE inhibitors
ARBs
NSAIDs
Glucocorticoids
Immune-suppression
Chloroquine
Hydroxychloroquine
Azithromycin
Zinc
Vitamin C

Interim Monitoring.

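### When baseline QTc is partly missing, the SAP's 80% rule for choosing the QTc test gives up precision that one analysis of all patients with a follow-up QTc would keep

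*SAP*

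**What the plan says.** The SAP's Safety reporting section treats the two QTc measurements differently. The follow-up value was planned for everyone: "QTc was monitored at 24–48h after randomization as a study procedure". The baseline value was not: "QTc monitoring at baseline was not mandatory but was described where it was available".

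The between-arm test then depends on how many baseline values exist. "If the baseline QTc is available in at least 80% of participants, an analysis of covariance will be performed", comparing follow-up QTc with adjustment for baseline. "Otherwise, a 2-sample t-test will be used to compare the follow-up QTc levels".

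Baseline values also have a descriptive use whichever test is run: "We also described the change between baseline and 24–48h after randomization in QTc", summarised by arm.

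The SAP does not say how a patient without a baseline QTc enters the ANCOVA. Its Missing Data section concerns outcomes. For the primary and key secondary outcomes it says "Hence, our primary analyses will be restricted to non-missing observations, without imputation". Its promise for other endpoints reads "Similar single imputation rules will be devised for sensitivity analyses of secondary efficacy endpoints", and QTc is a safety measure. Nor does the rule say whether its 80% is counted among all randomised patients, the safety population, or patients with a follow-up EKG.

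**The concern.** Partial availability is the case to expect. Protocol Appendix 1 schedules an EKG at 24–48 hours and none at baseline, Protocol 6.3 rules out protocol-specific tests at screening, and the QTc exclusion in Protocol 4.3 applies only where a value is already known. By contrast, Protocol 5.3 and 5.4.1.1 provide a research EKG at 24–48 hours if no clinical one was done. So the outcome is planned for all patients while the covariate is patchy.

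In that situation each branch gives something up. Below 80%, the t-test makes no use of the baseline values in hand. At 80% or above, ordinary ANCOVA software omits patients whose covariate is missing unless told otherwise, and the SAP does not tell it otherwise. Near the cut, a few clinical EKG orders decide which test is run and on whom.

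At stake is the precision of the group comparison of QTc. Protocol 5.4.1 names QTc prolongation as a risk of both drugs, and it is the reason for the scheduled study EKG.

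**Working it through.** **Plan's own figure.** There is none to reproduce. The documents give no QTc effect size, standard deviation, correlation, power or availability.

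**Inputs**
- f, the share of patients with a baseline QTc: not given; shown at 30%, 79%, 80% and 95%.
- r, the correlation of baseline with follow-up QTc: not given; assumed 0.5 to 0.7, with 0.3 and 0.8 as outer checks.
- N = 300, the target in the SAP's Sample size and power section. Equal arms and a follow-up QTc in every patient are assumed. N is used only for counts and power.

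**Formulas.** Variance of the treatment difference, relative to a t-test on all patients with a follow-up QTc, taking missing baselines as unrelated to QTc:
- t-test: 1
- complete-case ANCOVA: (1 − r²)/f
- ANCOVA on all patients, missing baselines set to the mean, plus a missing-baseline indicator: 1 − f·r²
- likelihood model, combining patients with and without a baseline: 1/[f/(1 − r²) + (1 − f)]

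**Results**

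| f | r | Planned test | Indicator ANCOVA | Likelihood | Planned ÷ indicator |
|---|---|---|---|---|---|
| 30% | 0.5 | t-test, 1.000 | 1 − 0.30×0.25 = 0.925 | 0.909 | 1.081 |
| 30% | 0.7 | t-test, 1.000 | 1 − 0.30×0.49 = 0.853 | 0.776 | 1.172 |
| 79% | 0.5 | t-test, 1.000 | 1 − 0.79×0.25 = 0.8025 | 0.792 | 1.246 |
| 79% | 0.7 | t-test, 1.000 | 1 − 0.79×0.49 = 0.613 | 0.568 | 1.632 |
| 80% | 0.5 | ANCOVA, 0.75/0.80 = 0.938 | 1 − 0.80×0.25 = 0.800 | 0.789 | 1.172 |
| 80% | 0.7 | ANCOVA, 0.51/0.80 = 0.638 | 1 − 0.80×0.49 = 0.608 | 0.565 | 1.049 |
| 95% | 0.5 | ANCOVA, 0.75/0.95 = 0.789 | 1 − 0.95×0.25 = 0.7625 | 0.759 | 1.035 |
| 95% | 0.7 | ANCOVA, 0.51/0.95 = 0.537 | 1 − 0.95×0.49 = 0.5345 | 0.523 | 1.004 |

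At f = 100% the ANCOVA drops nobody, and at f = 0% there is no baseline to use, so the loss is nil at both ends.

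**In patients.** With N = 300, complete-case ANCOVA at 80% omits 0.20 × 300 = 60 patients. The t-test at 79% leaves 0.79 × 300 = 237 baseline values out of the test.

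**In power.** Take the difference (0.323 SD) at which the t-test on 300 patients has 80% power. At r = 0.5:
- f = 79%: 80.0% under the rule, 87.8% with the indicator, 88.3% with the likelihood model.
- f = 80%: 82.5%, 87.9% and 88.4%.

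**Does the 80% cut pick the more precise planned test?** Complete-case ANCOVA beats the t-test when (1 − r²)/f < 1, that is r > √(1 − f). At f = 0.80 this is r > √0.20 = 0.447. At r = 0.4 the ANCOVA variance is 0.84/0.80 = 1.05, worse than the t-test.

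**Is the indicator version always better?** It is less precise than complete-case ANCOVA when r² > 1/(1 + f). At f = 0.80 this is r > √(1/1.8) = 0.745. At r = 0.8 the variances are 0.488 (indicator), 0.450 (complete-case) and 0.413 (likelihood).

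**Bias.** The t-test, complete-case ANCOVA and indicator ANCOVA were simulated with 2,500 runs per setting and a true difference of 0.300 SD, the same for all patients. Mean estimates ran from 0.296 to 0.303, including settings where missingness depended on baseline QTc. The likelihood combination was not in these runs. It averages two randomised contrasts, one among patients with a baseline and one among those without, so the same reasoning applies to it.

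**The case against.** The strongest reply is that both planned tests are standard and valid, the rule was fixed by personnel whom the SAP describes as blinded, and QTc is neither a primary nor a secondary endpoint. The SAP presents its safety p-values as nominal and crude, and the individual QTc check in Protocol 5.4.1.1 does not depend on any group test. All of this stands. It limits the importance of the point but does not restore the lost precision.

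Some stronger readings are tempting, and the documents do not support them:
- A reader might infer that the rule always discards data. It does not at 0% or 100% availability, and near 100% the loss is small. Baseline values left out of the t-test still appear in the descriptive summaries.
- A reader might take complete-case analysis as the SAP's stated method. The SAP is silent; dropping patients is the usual default, not its wording.
- A reader might infer bias because clinicians chose whom to record. That selection precedes treatment, so it should fall alike on both arms, and the simulations showed no distortion. What changes is the population analysed.
- A reader might see a data-driven choice of test that inflates type I error. The switch turns on availability, not on QTc results.
- A reader might take 25–63% as the expected loss. That is the size just below the cut, where it peaks; actual availability is not reported.

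**Conclusion.** The point holds as a loss of precision under partial baseline availability, together with a method and analysed population that depend on how many baseline EKGs happened to be ordered. For correlations of 0.5 to 0.7, the excess variance over indicator ANCOVA ranges from about 0.4% (95% availability, r = 0.7) to 63% (79% availability, r = 0.7). If the correlation is below about 0.45, the rule at 80% availability selects the less precise of its own two tests.

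This rests on three assumptions: the correlations, which the documents do not give; default omission of patients without a baseline; and a follow-up QTc in essentially all patients. It concerns one supporting safety comparison and has no bearing on the primary analysis.

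**What to change.** Delete the 80% switch and prespecify one baseline-adjusted comparison of all patients with a follow-up QTc. Either of two methods would serve:
- a likelihood model for baseline and follow-up QTc, which is at least as precise as either planned test at every correlation examined; or
- ANCOVA on treatment, baseline QTc with missing values set to the mean, and a missing-baseline indicator. By the formula above this is never less precise than the t-test, but it is less precise than complete-case ANCOVA if the correlation exceeds about 0.745 at 80% availability.

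Name the analysis set, and report the unadjusted difference as support. The cost is a sentence or two in the SAP and slightly more analysis work. No new data or extra EKGs are needed.
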